5.3 Method of Assignment/Randomization (if applicable)

Using a 1:1 randomization procedure, eligible individuals will be assigned to either the 1) supportED group (n=30) or 2) control group (n=30). Randomization will be stratified by assigned sex at birth (male or female).

5.4 Device Calibration

There is no necessary calibration process as supportED is a webbased game. If there are any concerns or issues with the functionality of the game, [name] of Digital Mill will be available to assist. Participants will answer study related questions through a secured data management system, RedCap. The game itself will not be utilized to record any data.

5.5 Storage Conditions

supportED is a web-based game that will be delivered to participants via tablets, phones, or desktops. Participants will engage with the game under the supervision of the study team to ensure proper use of the game and care for the devices. Although our game does not collect any identifiable data, tablets will be locked and stored in a secure location.

5.6 Concomitant therapy

N/A there are no restrictions

5.7 Restrictions

Participants will engage with the device for a restricted period of 45 minutes (one-time session).

6 - Study Design

6.1 Study Design

The protocol will be conducted over the course of two years. The outline below highlights the study design.

Formative Work: We will conduct focus groups to inform the development of a digital game and discuss approaches to enhance user experiences, acceptability, and feasibility of the game. First, we will conduct six focus groups with a total of 30 participants, including 10 high-school-aged adolescents, 10 college-aged youth, and 10 providers, to inform the content of the videogame with a focus on content related to potential warning signs, coping strategies, and seeking help to prevent suicidal thoughts and behaviors among youth who misuse opioids. Focus groups will occur in-person or via Zoom over the course of six months. Each group will meet for approximately 1-1.5 hours after school hours. The study will be introduced to parents/guardians and students and then, if interested in participating, information sheets will be provided via paper form or electronically. When the study is introduced to parents/guardians and students, we have always stressed that a stipulation of our studies requires reliable transportation to/from our studies if conducted in person. In certain cases where transportation is not available by family or school, we will provide a bus pass.

Focus groups will be approximately 60-90 minutes. A semi-structured focus group guide will be developed, pilot tested and used in focus groups. The focus group guide will align with constructs from a safety planning intervention,^{5,6} a well-recognized, evidence-based suicide prevention intervention, and include questions related to potential warning signs of emotional distress, coping strategies, and seeking help to prevent suicidal thoughts and behaviors among youth who misuse opioids. Focus groups will be led by a facilitator, who is also a certified school counselor and licensed professional counselor, and a co-facilitator who will take field notes. Focus groups will be audio-recorded. Transcripts will be transcribed verbatim by a third-party transcription service who our Lab has worked with prior. All participants will receive instructions on not using identifiable information (e.g., names, school, peer/colleague names, etc.) while being audiotaped and will be provided a study number prior to the start of audiotaping. Participants will be instructed to state their study number prior to speaking. Audiotapings will be transcribed and will be destroyed 24 months after the completion of the study and after review of their content has been completed. Transcriptions will not be sent to other institutions and will not be used for purposes other than this study and future publications related to this study. Should any identifiable information be shared in the focus groups, it will be redacted from transcripts. Participants will receive a \$25 gift card to participate.

We will follow the same protocol for play-testing focus groups to finalize the game.

Pilot Study: To examine usability, acceptability, and feasibility, we will conduct a pilot study. We will enroll 60 high-risk adolescents who attend one of our partner school sites. We will also explore proximal outcomes.

Our research team will be trained by [name] team and the Pitt Methods workshop prior to commencing the study in all procedures, risk and protection methods, and safety related to conducting suicide **prevention** research. Eligible individuals will be assigned to either the 1) supportED group (n=30) or 2) control group (n=30). Both groups will also receive NIDA/NIMH pamphlets on substance misuse and mental health for youth at the end of the session. Prior to receiving pamphlets, those in the supportED group will engage with the game for one session (~45min) while the control group will engage with a non-health-related game for the same duration. Given schools do not have a standardized approach to address suicide prevention, we opted to use an attention/time control condition.

Participants will use a dedicated device (e.g., tablet) to access their digital experience on the web. The research staff with [name] always there will be present to monitor gameplay, to provide support, if needed, and to field questions in person. A school-based provider will be present for direct referrals, as needed. The total duration and number of sessions is consistent with those found in safety planning and with the amount adolescents engaged with our empowerED game.^q To pilot the feasibility of protocols, we will collect proximal outcomes, as possible mechanisms for behavior change. Proximal outcomes include but are not limited to the following measures: 1) intention to use safety planning; 2) coping strategies; and 3) severity of suicidal thoughts and associated risk factors (e.g., pessimism, helplessness, limited social support, and despair). We will also measure severity of suicidal ideation and attempts

We will collect participant demographic data including self-reported sex at birth, gender identity, sexual orientation, race, and ethnicity to determine subgroup similarities and/or differences. We will collect assessment data before and immediately after the participants engage with the game as well as at 3 months following gameplay. The primary outcomes of the proposed study are to examine: 1) the usability (e.g., ease of use) and acceptability (e.g., gameplay satisfaction) of the game among adolescents; and 2) the feasibility of delivering the game and piloting protocols in schools. To assess usability, acceptability, and feasibility, directly following supportED game completion, we will collect focus group data on participants' experiences. The following proximal outcomes, as mechanisms for behavior change, will be measured: 1) intentions to use safety plan;^r 2) coping strategies through adaptive and maladaptive subscales;^s and 3) severity of suicidal thoughts and associated risk factors using the Concise Health Risk Tracking Self-Report (CHRT-SR) comprised of the following subscales: Propensity (including domains of Pessimism, Helplessness, Limited Social Support, and Despair), Impulsivity, and Suicidal Thoughts.^t We will measure substance misuse in past 30^u days as a possible mediator. These scales will be self-reported by adolescents.

All of our data will be self-reported data; therefore, we will use data collection methods such as confidential self-administration that have been effective in our trials to minimize social desirability bias in self-reported data. Participants will receive \$25 gift cards as compensation for completion of assessments at each timepoint (e.g., baseline/post-game and 3-month follow up)

The Yale University Human Subjects Committee (the committee that reviews, approves, and monitors research on human subjects) may inspect study records. All published results will be group data. Information that will be collected during the focus group interviews will be erased 24 months after the completion of the study and after review of their content has been completed.

- 1. Formative and development work: (1 year)**
 2. We will work iteratively with our target audience of 16-19-year old adolescents within schools, college-aged youth for a reflection of that age range, and school-based mental health providers to develop videogame content, collecting qualitative data for the videogame and refining our logic model with input from 4 focus groups of 5 high school-/college-aged youth each (n=20), aged 16-19 and 2 focus groups of 5 school-based mental health providers aged 18-80 (n=10).
 3. We will create the “Game Playbook” specific to this new digital game. Game Playbooks are our game manuals. We create behavior change gameplay manuals to accommodate the specific needs of a multi-disciplinary game development team. The playbooks outline the theoretical foundations and gameplay elements. This ensures targeted theoretical principles and behavior change mechanisms and constructs are included in the videogame.
 4. We will build the new digital game by creating new content, developed from focus groups and from the suicide and opioid misuse prevention literature, for our game development team, DigitalMill, Inc.
 5. We will conduct play-testing focus groups with input from focus groups of 5 high school-/college-aged youth each (n=20), aged 13-19 and focus groups with adults who specialize in addiction medicine 18-80 (n=10) to assess user experience (e.g., acceptability and usability) and feasibility of protocol to prepare for a larger pilot study that will require a new protocol (N=60).
- 6. Pilot Study:**
 7. We will conduct a pilot study with (N=60) adolescents between the ages of 13-19. We will examine the usability and acceptability of the game among adolescents, and the feasibility in conducting the study in schools.
Inclusion criteria: For the pilot study, participants must: 1) attend a high school that has a school-based behavioral provider; 2) be between the ages of 13-19; 3) be

fluent in reading English as determined in consent process; 4) be willing to sit for a single session to complete pre-/post-assessments, engage with the game (~45min), and participate in a post-gameplay focus group (if in the experimental group) for 60min; and 5) provide assent and parental/guardian consent (if < age 18).

8. We will also assess proximal outcomes as potential means for behavior change in supportED vs. control group at 3 months. Examples include but are not limited to: 1) intentions to use safety plan; 2) coping strategies; and, 3) suicidal thoughts and associated risk factors (e.g., pessimism, helplessness, limited social support, and despair).

6.2 Study Duration

The anticipated duration of this study will be two years. Participants will engage in focus groups over one-year period for approximately 60-90 minutes each. Participants will participate in a pilot study in year 2.

6.3 Outcome Variables

Formative Work: Our study is qualitative by nature. We will explore participants' perceptions on their peers' or students' warning signs, coping strategies, and resources to seek help related to substance misuse and suicide prevention as outlined in safety planning. We will also ask questions about what they would like in a technological game with regard to usability and acceptability. We will ask providers questions about feasibility. Feedback on what participants view as acceptable/feasible will be critical to developing successful technological games targeting suicide.^v

Pilot Study:

The findings from the proposed study have strong potential for positively impacting adolescents who report opioid/substance misuse and who may be at greater risk for suicidal thoughts and behaviors. It will be the first to provide evidence that a suicide prevention videogame offers an engaging approach and is feasibly conducted in schools with adolescents. With schools seeking technology-based approaches and videogames providing an engaging platform for adolescents, the proposed study has the potential to serve as a necessary first step for long-lasting implications on the health and well-being of adolescents.

6.4 Study Procedures

Formative Work: Participants will engage in six 60-90-minute focus groups led by a licensed professional counselor, and a co-facilitator who will observe and take notes. Focus groups will be audio-recorded and held in a private room within the school if conducted in a school or held via Zoom if conducted virtually. Participants will be asked questions developed from a semi-structured focus group guide, which will first be pilot tested. Questions will be grounded in constructs of a safety planning intervention^w as well as self-determination^w and social cognitive theories^x and techniques used in Motivational Interviewing.^y Participants will

be asked to not share any identifiable information. Should any be shared, it will be redacted from transcripts. Participants will receive a \$25 gift card to participate. Same procedures will be in place for play-testing focus groups.

Pilot Study: We will pilot test *supportED* to examine usability, acceptability, and feasibility. We will enroll 60 adolescents who attend one of our partner school sites. To determine feasibility in piloting protocols, we will also explore proximal outcomes. Eligible individuals will be assigned to either the 1) supportED group (n=30) or 2) control group (n=30). Both groups will also receive NIDA/NIMH pamphlets on substance misuse for youth at the end of the session. Prior to receiving pamphlets, those in the supportED group will engage with the game for one session (~45min) while the control group will engage with a non-health related game for the same duration. Given schools do not have a standardized approach to address suicide prevention, we opted to use an attention/time control condition. Participants will use a dedicated device (e.g., tablet) to access their digital experience on the web. The research staff with [name] always there will be present to monitor gameplay, to provide support, if needed, and to field questions in person. A school-based provider will be present for immediate referrals, as needed.

The total session lasting approximately 90 minutes. The facilitator will ask adolescents to sign assent form and provide clarification or answer any questions about the study procedure. Prior to the session, we will share flyers with educators, school-based providers, and our youth advisory board who will share with participants. Students may then share with other students (e.g., snowball sampling). The flyers contain a QR code for students to input their first/last name, phone number, and email address. If they are younger than 18, they must input parent/guardian first and last name, phone number, and email address.

Research staff will then contact them to obtain consent/e-consent. When needed, study staff will be available to parents/guardians should they have any questions. Before students are able to participate in the research study, they must have a signed assent and parent/guardian consent if under 18.

When the gameplay portion of the session begins, participants will play the game on an iPad or desktop device. A member of the research team or the facilitator will be there to provide assistance at all times. After completing the game, adolescents will be asked to participate in a questionnaire session and focus group about their overall gameplay experience. This will be facilitated by one of the members of the research team. The responses of the participants will be gathered and documented as data, which will be kept confidential. If at any point a student is flagged as moderate to high risk due to concerns related to substance misuse, depression, and/or suicide, they will be immediately referred to the school-based provider who will be on site during baseline and 3-month follow up. If a student is triggered by the sensitive nature of the topics, their school-based provider will be able to provide emotional support and/or referral to services. These same procedures will be utilized in local CT schools and in Miami-Dade County public schools.

DATA COLLECTED: We will collect name of student and parent/guardian if under 18, their email addresses and phone numbers to obtain assents/consents. This information will be de-identified prior to the start of research. We will collect participant demographic data including self-reported sex at birth, gender identity, sexual orientation, race, and ethnicity to determine subgroup similarities and/or differences. We will collect assessment data before and immediately after the participants engage with the game as well as at 3 months following gameplay. The primary outcomes of the proposed study are to examine: 1) the usability (e.g., ease of use) and acceptability (e.g., gameplay satisfaction) of the game among adolescents; and 2) the feasibility of delivering the protocols and procedures of conducting the study in schools. To assess usability, acceptability, and feasibility, directly following supportED game completion, we will collect focus group data on participants' experiences. The following proximal outcomes, as mechanisms for behavior change, will be measured including but not limited to: 1) intentions to use safety plan;⁷⁴ 2) coping strategies through adaptive and maladaptive subscales;⁷⁵ and 3) severity of suicidal thoughts and associated risk factors using the Concise Health Risk Tracking Self-Report (CHRT-SR) comprised of the following subscales: Propensity (including domains of Pessimism, Helplessness, Limited Social Support, and Despair), Impulsivity, and Suicidal Thoughts. We will measure substance misuse in past 30 days as a possible mediator. These scales will be self-reported by adolescents. Participants will receive \$25 gift cards as compensation for completion of assessments at each timepoint (e.g., baseline/post-game and 3-month follow up).

6.5 Withdrawal Procedures

Participation in the formative work and pilot study is voluntary. Participants may withdrawal at any point. This will be explicitly stated prior to the start of each focus group, interview, or research session.

6.6 Locations/Facilities

Formative: The study will be conducted virtually via Zoom and/or at previously long-standing and established partner school sites. We will recruit from existing partnerships in Connecticut and Miami- Dade County schools, such as but not limited to Maloney (N=1191), Bassick (N=970), Ronald W. Reagan Doral (N= 1440), Miami Lakes Educational Center (N= 1015), Alonzo and Tracy Mourning (N=1528), School for Advanced Studies West (N=119), and Barbara Goleman (N=2882).

Pilot Study: The study will be conducted virtually via Zoom and/or at previous long-standing and established partner school sites. We will recruit from existing partnerships in Connecticut and Miami-Dade County schools, such as but not limited to Maloney (N=1191), Bassick (N=970), Ronald W. Reagan Doral (N= 1440), Miami Lakes Educational Center (N= 1015), Alonzo and Tracy Mourning (N=1528), School for Advanced Studies West (N=119), and Barbara Goleman (N=2882).

6.7 Data Collection

Formative Work: A research assistant will take notes during the focus groups, and a third-party transcription service, who our lab has worked with prior, will transcribe audio recordings verbatim. We will review field notes and focus group transcripts.

Pilot Study:

Currently our game does not record ANY personal information or even individual game information. We do not ask for a personal registration or login.

Twine by default does save information locally to the device running the Twine game off the Web server. No information is saved server-side and local information can be removed by deleting local-storage using the Web browser command to do so.

We envision most, if not all, players playing through an entire sitting in one session so saving locally shouldn't be a need, and devices will have local saves wiped if under-the-control of the research team.

We are considering disabling saves as well. However, Twine does maintain some saved state during play and it likely is cached (locally of course)

We MAY however implement the following depending on further IRB guidance:

1. A 'simple' password that blocks the site where the game is played from the public internet. This password would not be individual but would be a simple single password that any participant would need to know to enter the page.

This password would be changed periodically and would cease to work overall when the site was closed after initial trials.

2. We may add server-side recording of event-based analytics (i.e. user choices)

This data would be de-identified automatically because there would still be no initial login using an personally identifiable account or token.

We are considering using Google Analytics for this purpose or saving data to a Google Sheet.

In all cases of such analytics recording we would include a page accessible to all player (perhaps even requiring an acknowledgement) that their gameplay data is saved but is not identifiable.

There are no other plans or default actions that record player actions / data. There is no personalized login system that could enable such identifiable data.

Specific practices would be made to reduce the proliferation or retention of even unidentifiable game data in the short term (e.g. wiping local browser storage) and on a long term basis deleting long-term analytics data once its use for research and analysis is completed.

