4.4 Recruitment Procedures

Formative Work: Participants will receive a \$25 gift card to participate in focus groups and playtesting sessions. Flyers will be circulated throughout schools.

Pilot Study: For the pilot study, participants will receive a \$25 gift cards as compensation for completion of assessments at each time point. We will share with educators, school-based providers, and our youth advisory board who will share with students. Students may then share with other students (e.g., snowball sampling). The flyers contain a QR code for students to input their first/last name, phone number, and email address. If they are younger than 18, they must input parent/guardian first and last name, phone number, and email address. Research staff will then contact them to obtain consent/e-consent. When needed, study staff will be available to parents/guardians for information sessions should they have any questions.

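### Nothing in the plan closes the supportED web page between the session and the 3-month assessment, or asks students whether they played it in that time

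*Combined protocol and SAP*

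**What the plan says.** **Intended exposure.** Section 5.7: "Participants will engage with the device for a restricted period of 45 minutes (one-time session".

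**Access to the game.** Section 6.7 says of the game: "We do not ask for a personal registration or login". Access control appears only under the lead-in "We MAY however implement the following depending on further IRB guidance". The first item there is "A 'simple' password that blocks the site where the game is played from the public internet". It would be shared: "This password would not be individual but would be a simple single password that any participant would need to know to enter the page". It would be changed from time to time and "would cease to work overall when the site was closed after initial trials", with no date tied to a student's follow-up. Play is not recorded by default. The analytics that might be added would carry no personal identifier.

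**Who could share access.** Section 5.3 randomises individual students 1:1, 30 per arm, stratified by sex at birth only. Section 7.1 spreads the 60 students over 6-10 high schools. Section 4.4 says of the recruitment flyer: "Students may then share with other students (e.g., snowball sampling".

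**Setting.** Section 5.2 has research staff prepare dedicated devices as control or game and monitor play. Section 5.5 includes phones among the delivery devices and has tablets locked away. Section 6.6 allows the pilot to run over Zoom as well as at schools.

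**Use of the data.** Section 7.2 compares the arms from baseline to 3 months with a mixed model, labels the analyses exploratory, and applies a 0.05 threshold. Section 6.8 lists the measures. None asks about play after the session.

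**The concern.** The 3-month contrast is meant to compare one session of supportED with one session of an unrelated game. That holds only if controls do not reach supportED during the three months and supportED students do not return to it. The plan describes no step that secures either condition once the session ends, and no question that would show whether they held.

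Two different things could go wrong. A control who plays receives some of the intervention, which pulls the arms together. A supportED student who replays receives more than the stated single session, so the contrast no longer describes that dose. Replay would also make gameplay duration, one of the factors examined in section 7.2, wrong for those students.

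Coping is the outcome most exposed. Section 6.8 places the Brief COPE at baseline and 3 months only, so it has no reading directly after play that escapes the problem.

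**Working it through.** The documents give no effect size, SD, power or dropout for the pilot, so there is no figure to reproduce. The check has two parts.

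**1. Is later access possible, and would it be seen?**

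- *Barrier:* no login (6.7). The password is optional, and if used it is a single one that participants would need to know (6.7).
- *Closing date:* after the initial trials, with no link to the 3-month visits (6.7).
- *Contact between arms:* 60/10 = 6 to 60/6 = 10 students per school on average, or about 3-5 per arm if the split within a school is even. School is not a stratification factor (5.3), so the split will vary. Both arms can be present in one school.
- *Devices outside staff control:* the Zoom option (6.6) would presumably need the address on a device that staff do not hold. Phones are a listed delivery device (5.5). Section 6.7 makes the wiping of saves conditional on the device being under the team's control, which allows that some are not.
- *Record of later play:* none by default, none attributable to a student through the optional analytics (6.7), and no questionnaire item (6.8).

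Later access is therefore possible and would go unrecorded.

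**2. How much could it matter?** Every value here except the 30 per arm and the 0.05 threshold is assumed: true effect d = 0.50 SD, two-sided test (the plan does not state sidedness), SD = 1, no dropout, normal approximation.

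- SE of the difference = √(2/30) = 0.258 SD.
- Power ≈ Φ(d/SE − 1.96). At d = 0.50: Φ(1.936 − 1.960) = 49%.
- Control play: a share c of controls gains the full effect, so the observed effect is d(1 − c).
- Replay: a share r of supportED students gains an extra fraction g of the effect, so the observed effect is d(1 + r·g).

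| Scenario | Observed effect (SD) | Power |
|---|---|---|
| Neither | 0.50 | 49% |
| c = 10% | 0.50 × 0.9 = 0.45 | 41% |
| c = 20% | 0.50 × 0.8 = 0.40 | 34% |
| c = 30% | 0.50 × 0.7 = 0.35 | 27% |
| r = 10%, g = 0.5 | 0.50 × 1.05 = 0.525 | 53% |
| r = 30%, g = 1.0 | 0.50 × 1.30 = 0.65 | 71% |

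With both at once (c = 20%, r = 20%, g = 0.5): 0.50 × (1 + 0.10 − 0.20) = 0.45 SD.

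For other true effects, c = 20% takes 0.30 to 0.24 and 0.80 to 0.64.

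For scale, dilution of 0.05-0.15 SD is 0.05/0.258 = 0.2 to 0.15/0.258 = 0.6 of one standard error. The 95% half-width is 1.96 × 0.258 = 0.51 SD.

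**The case against.** The case on the other side is substantial.

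- **Only an exploratory comparison is touched.** Sections 6.1 and 6.4 make usability, acceptability and feasibility primary, with focus group data collected straight after play. Section 5.1 says the study is not powered for efficacy, and section 7.2 calls the outcome analyses exploratory. This stands and limits the weight of the point. It does not remove it, because section 7.2 still tests a between-arm hypothesis at 0.05.
- **Safeguards exist.** Prepared, supervised devices make leakage from a school session less likely. This stands for school sessions. It does not cover a Zoom session or the months afterwards.
- **The shifts are small beside the sampling error.** True at the assumed values. But sampling error is reported with the estimate, whereas unrecorded exposure would not be.
- **The password is a disclosed, pending IRB decision.** Also true, so any change should be made subject to that decision.

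A reader might go further and infer four things that the documents do not support. They do not say that students see or receive the web address. They do not show that the two arms share friendship groups: section 4.4 says only that students may pass on a flyer. They do not show a bias in a known direction, because control play and replay act in opposite directions. Under replay, a comparison by assigned arm still estimates the effect of offering the game. Nor is later play beyond detection: a question at 3 months would pick it up by self-report.

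**Conclusion.** The gap is real and modest. Section 5.7 states a one-session exposure, but nothing described in the plan holds that limit after the session or measures departures from it. Access by controls and replay by supportED students are both plausible, in unknown amounts. The net effect on the 3-month contrast therefore has no known sign or size. The range of 0.45-0.35 SD for a true 0.50 SD rests on assumed exposure of 10-30% of controls, with full benefit to each. It illustrates dilution only and is not an estimate.

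Usability and acceptability ratings taken directly after play are unaffected. The reason to act is that the information cannot be fully recovered once follow-up has ended, while collecting it costs almost nothing. Whether exposure can be confined within a school is also a useful feasibility finding for a later trial.

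**What to change.** **Section 6.7, subject to IRB agreement.**

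- Change the password from something the team may add to something it will add.
- Have staff enter it on study devices, in place of the present description in which participants need to know it. Making a shared password mandatory is not enough if students hold it, because they can pass it on or reuse it.
- Change it after each session, and state how this works for any Zoom session.
- Keep the site closed to the public until the last 3-month assessment is complete.

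**Section 6.8.** Add one 3-month item in both arms, such as: *Have you played or been shown this game since the session?* The item should make clear to controls that it refers to supportED.

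**Section 7.2.** Report the answers by arm and prespecify a sensitivity analysis of the 3-month contrast that uses them. Because later play is a student's own choice after randomisation, the comparison by assigned arm should remain the main one.

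**Cost.** Staff must enter and change a password, and students answer one more question. The item relies on self-report and may undercount.
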